Amendment 1	11 May 2021	
The primary purpose of the amendment is to add 1-2 additional sites to boost enrollment and incorporate feedback received from the United States (US) Food and Drug Administration (FDA).
 
In addition, clarifications, reconciliations, administrative and typographical modifications were made.
 
1. “Single-center study” was replaced by “Multicenter study” throughout the protocol.2. As study population is outpatients with moderate COVID-19, a Toxicity Grading Scale for Healthy Adult and Adolescent Volunteers Enrolled in Preventive Vaccine Clinical Trials will be used for grading of AEs associated with systemic (general) abnormalities, vital signs, illnesses and lab abnormalities instead of CTCAE v.5.0 (FDA recommendation). Full guidelines may be obtained at https://www.fda.gov/media/73679/download .3. Section 1.1. SYNOPSIS:
• Study Description: It was clarified that CX-4945 neither impacts on the effectiveness of other antiviral drugs nor contributes to the emergence of viruses with reduced susceptibility to the drug, since CX-4945 targets the host protein kinase.• Study Description. Number of enrolled patients was changed from “20” to “approximately 20” to add flexibility in case any patients to be replaced due to protocol violation or discontinue the study prior to the first dose, etc.• Secondary Objectives and Endpoints: The secondary objective to evaluate time to clinical recovery measured by time to resolution of clinical

		
signs and symptoms was split to two objectives measured separately by duration of clinical signs and duration of clinical symptoms correspondingly (FDA recommendation).
 
• Secondary Objectives and Endpoints: The secondary objective to evaluate CX-4945 PK was updated to clarify that PK samples will be collected from the first four patients randomized to treatment arm A. Further PK collection is not required, as enough data have been collected in two CX-4945 studies to proceed with PK analysis.• Secondary Objectives and Endpoints (other clinical benefit of treatment with CX-4945): evaluation of disease progression and health improvement measured by the ordinal 8- Point Clinical Progression Outcome Scale was clarified.• Secondary Objectives and Endpoints (other clinical benefit of treatment with CX-4945): Outcome measure for changes of SpO2 was updated to number of days to normalization of oxygen saturation (categorized as <96% versus ≥96%).• Study Duration was changed from 5 months to 12 months due to enrollment challenges. 
4. Section 1.3: SCHEDULE OF ACTIVITIES
 
• Assessment for the requirement of mechanical ventilation, ECMO, non-invasive ventilation, or high-flow nasal cannula oxygen delivery was deleted as it was the same as clinical status assessment using the ordinal 8- Point Clinical Progression Outcome Scale.• PK collection was removed from the Schedule of Activities (SOA). PK samples will not be collected anymore, as enough data have been collected in two CX-4945 studies to proceed with PK analysis.• Numbers of footnotes were reconciled
--	--	---

		
• Footnote 14: It was clarified that Follow-up visits (Day 28, Day 45, and Day 60) may be performed via phone or telehealth only for recovered patients.• Day 2, Day 15, Day 16 and Day 17 visits were deleted from the SOA as these visits are required only for patients participating in the PK study. PK collection is not required anymore, as enough data have been collected to proceed with PK analysis. 
5. Section 2.1: STUDY RATIONALE
 
• Study Rationale was updated in accordance with the recent COVID-19 Treatment Guidelines of 8-Apr-21 (https://www.covid19treatmentguidelines.nih.gov). 
6. Section 2.4: RISK/BENEFIT ASSESSMENT
 
• It was added that CX-4945 does not impact the effectiveness of other antiviral drugs or contribute to the emergence of viruses with reduced susceptibility to the drug, since CX-4945 is an inhibitor of the host protein kinase. 
7. Section 3: STUDY OBJECTIVES AND ENDPOINTS
 
• The same changes were made in Section 3 as listed above under Item 3, bullets 4, 5, 6 and 7. 
8. Section 4.1: OVERALL DESIGN
 
• Addition to SOC: Patients progressed on treatment with monoclonal antibodies can be enrolled, if meet eligibility criteria. 
9. Section 5.1.1: INCLUSION CRITERIA
 
• The inclusion criterion #2: a timeframe of 7 days before Day 1 was specified for the positive screening PCR test required for eligibility evaluation.• The inclusion criterion #3: the names of the symptoms were aligned with those in the proposed patient-reported outcome (PRO) instrument (FDA recommendation).
--	--	---

		
• The inclusion criterion #9 was added: Patient must agree not to participate in another clinical trial for the treatment of COVID-19 during the study period until disease progression, hospitalization, withdrawal from study treatment or 28 days after the start of the study, whichever occurs first. 
10. Section 5.1.2: EXCLUSION CRITERIA
 
• The exclusion criterion #5 of “concomitant treatment with another investigational drug from Day 1 through Day 28” was revised to “concomitant treatment with another investigational drug” as it should not be applied after treatment initiation (FDA recommendation).• The exclusion criterion #7 was added: Any active or recurring clinically significant hepatic disease (FDA recommendation). 
11. Section 6.1.5: CX-4945 DOSE MODIFICATION
 
• Table 3, CX-4945 Dose Modification and Management for Potential Toxicities: Standardized toxicity grading scale (CTCAE v.5.0) was modified to Toxicity Grading Scale for Healthy Adult and Adolescent Volunteers Enrolled in Preventive Vaccine Clinical Trials https://www.fda.gov/media/73679/download (FDA recommendation)• Reasons for dose discontinuation were listed 
12. Section 7: STUDY COMPLETION OR DISCONTINUATION
 
• This Section was revised to reconcile discrepancies and clarify difference between study discontinuation and withdrawal from treatment (FDA recommendation). 
13. Section 8.2.2: EFFICACY/ANTI-VIRAL ACTIVITY ASSESSMENT
 
• COVID-19-related symptoms and signs will be evaluated separately for recovery assessment (FDA
--	--	---

		
recommendation). Section 8.2.2.1 describes COVID-19-related symptoms assessment. Section 8.2.2.2. describes clinical signs assessment. Heart rate was added to clinical sign assessment (section 8.2.2.2). It was added that any abnormal signs or symptoms not related to COVID-19 and caused by other conditions documented in medical history and started before COVID-19 will not be included to recovery assessment. The patient can be considered as recovered, when these symptoms return to the previous (pre-COVID-19) values.
 
14. Section 8.3.3.1: SEVERETY OF AEs
 
As study population is outpatients with moderate COVID-19, a standardized toxicity grading scale was modified to reflect the study population. Toxicity Grading Scale for Healthy Adult and Adolescent Volunteers Enrolled in Preventive Vaccine Clinical Trials will be used for grading of AEs associated with systemic (general) abnormalities, vital signs, illnesses and lab abnormalities instead of CTCAE v.5.0 (FDA recommendation). Full guidelines may be obtained at https://www.fda.gov/media/73679/download . 
15. Section 9.2: DESCRIPTION OF STUDY OUTCOMES
 
Duplicate information has been removed and reference to Section 1.1. and Section 3 is added. 
16. Section 9.4: RANDOMIZATION
 
WebView IWRS has been removed as it not applicable for this study.
--	--	--

TABLE OF CONTENTS

	Page
1. PROTOCOL SUMMARY	14
1.1. Synopsis	14
1.2. Schema.....	20
1.3. Schedule of Activities (SOA)	21
2. INTRODUCTION AND BACKGROUND.....	23
2.1. Study Rationale.....	23
2.2. Background.....	24
2.3. CX-4945.....	25
2.4. Risks/Benefits Assessment	27
3. STUDY OBJECTIVES AND ENDPOINTS.....	28
4. STUDY DESIGN.....	32
4.1. Overall Design.....	32
4.2. Justification for dose	32
4.3. End of Study Definition	33
5. STUDY POPULATION	34
5.1. Patient Eligibility Criteria	34
5.1.1.Inclusion Criteria.....	34
5.1.2.Exclusion Criteria.....	35
5.2. Screen Failures	36
6. STUDY TREATMENT	37
6.1. Study Treatment Administration.....	37
6.1.1.Investigational Drug Product Description	37
6.1.2.Randomization.....	37
6.1.3.Dosing and Administration of CX-4945	37
6.1.4.CX-4945 Compliance.....	38
6.1.5.CX-4945 Dose Modifications	38
6.2. INVESTIGATIONAL PRODUCT SUPPLIES, STORAGE AND ACCOUNTABILITY	39

6.2.1.Investigational Product Supplies	39
6.2.2.Formulation, Appearance and Packaging.....	39
6.2.3.Product Storage and Stability	40

1. PROTOCOL SUMMARY

1.1. SYNOPSIS

Title:	A Phase II, Randomized and Controlled Investigator-Initiated Trial Evaluating Safety, Pharmacokinetics and Clinical Benefit of Silmitasertib (CX-4945) in Outpatient Adult Subjects with Moderate Coronavirus Disease 2019 (COVID-19)	
Study Description:	
COVID-19 is characterized by SARS-CoV-2-induced upregulation of host protein kinase CK2 that catalyzes phosphorylation of many proteins, modulating their activities in cellular processes. SARS-CoV-2 nucleocapsid directly targets CK2 and this viral-host protein interaction affects many vital processes in host cells contributing to dysregulated host immune response, viral survival, replication and spread to nearby cells. CX-4945 demonstrated anti-viral and anti-inflammatory efficacy in COVID-19 in vitro studies and remarkable clinical benefits under emergency IND authorization. As CX-4945 is an inhibitor of the host protein kinase CK2, it does not impact on the effectiveness of other antiviral drugs or contribute to the emergence of viruses with reduced susceptibility to the drug.
 
This is a Phase II multicenter, open-label, randomized two-arm parallel-group controlled study in approximately 20 subjects to evaluate safety and explore putative clinical benefits of CX-4945 1000 mg BID dose in patients with moderate COVID-19. It will be a two-arm trial comparing the SOC/supportive care alone to the SOC/supportive care in combination with CX-4945(allocation ratio 1:1).
	
Primary Objective and Endpoints:	Primary Objective	Primary Endpoint
	To assess safety and tolerability of CX-4945 administered orally twice daily to patients with moderate COVID-19	Adverse events occurring from randomization (Day 1) to Day 60 (including vital signs, physical findings, clinical laboratory, and ECG results) as characterized by type, frequency, severity [as graded by Toxicity Grading Scale for Healthy Adult and Adolescent Volunteers Enrolled in Preventive Vaccine Clinical Trials (https://www.fda.gov/media/73679/download)], timing, seriousness, and relationship to study therapy.
Secondary Objectives and Endpoints:	Secondary Objectives	Secondary Endpoints
	To compare time to normalization of COVID-19-related	Number of days from Randomization (Day1) to the day when the following clinical signs are back to normal (as evaluated at every visit during the treatment period (Day

	
clinical signs in CX-4945 treatment arm versus the control arm.
 
1, Day 4, Day 8, Day 11 and Day 14) and at Follow-up visits (Day 28 and Day 45):
 
○ Fever is $\leq 36.6^{\circ}\text{C}$ from axillary site, or $< 37.2^{\circ}\text{C}$ from oral site or $< 37.8^{\circ}\text{C}$ from rectal or tympanic site○ Respiratory rate is < 20 breaths per minute○ $\text{SpO}_2 \geq 96\%$ in room air without shortness of breath or dyspnea caused by COVID-19○ Heart rate < 90 beats per minute 
Note: If some signs listed above were caused by other conditions documented in the medical history and started before COVID-19, the patient can be considered as recovered, when these signs return to the previous (pre-COVID-19) values.

To compare duration of COVID-19-Related clinical symptoms in CX-4945 treatment arm versus the control arm.	
Number of days from randomization (Day1) to the day when:
 
● No key COVID-19-related symptoms scored higher than 1 as documented using a Patient Reported Outcome (PRO) instrument (a Patient Diary for Assessment of Common COVID-19-Related Symptoms – see Appendix 3), evaluated daily from Day 1 through Day 14 and at Day 28 and Day 45. 
Note: Each symptom is scored individually using the following response options and scoring values:
 
○ Items 1–18: None = 0; Mild = 1; Moderate = 2; and Severe = 3○ Items 19 and 20: Not at all = 0; 1–2 times = 1; 3–4 times = 2; 5 or more times = 3

[figure not shown]
		
○ Items 21-22: The same as usual = 0, Less than usual = 1, NO sense of smell/taste = 2. 
Note: If some symptoms were caused by other conditions documented in the medical history and started before COVID-19 (e.g. insomnia), the patient can be considered as recovered, when these symptoms return to the previous (pre-COVID-19) value.

	To evaluate preliminary evidence of anti-viral activity of CX-4945 as compared to the control arm.	
● Change in virologic measure:
● Proportion of patients with conversion of positive RT-PCR to negative RT-PCR from randomization (Day 1) through Day 28.● Time to SARS-CoV-2 viral clearance measured as number of days from positive RT-PCR collected at randomization (Day1) to negative RT-PCR.● Quantitative changes in viral load from randomization (Day 1) to Day 28. 
Note: RT-PCR/viral load tests will be performed at randomization (Day 1) and then on Day 8, Day 14 and Day 28.

	To evaluate the PK of CX-4945 when given at 1000 mg BID PO (Treatment Arm A only)	
● Plasma sample for PK assessment are collected at the following timepoints from the first four patients randomized to treatment arm A:
○ Day 1: pre-dose, 1, 2, 3, 6 and 24 hours post Day 1 morning dose.○ Day 14: pre-dose, 1, 2, 3, 6, 24, 48 and 72 hours post Day 14 morning dose.

		
Note: The following PK parameters will be calculated: Cmax, Tmax, AUC_{0-T}, AUC₀₋₆, and T_{1/2}

	To evaluate other Clinical Benefit of treatment with CX-4945 relative to the control arm	
• All-cause mortality status – the number of deaths occurred in each treatment group from Randomization (Day 1) through Day 60.• Number of respiratory failure (i.e., need for mechanical ventilation, ECMO, noninvasive ventilation, or high-flow nasal cannula oxygen delivery) occurred in each treatment group from Randomization (Day 1) through Day 45.• Number of patients hospitalized in each treatment arm from Randomization (Day 1) to Day 45• Number of days to normalization of oxygen saturation level measured by pulse oximeter at Randomization (Day 1), Day 4, Day 8, Day 11, Day 14, Day 28 and Day 45 and categorized as <96% versus ≥96%. Proportion of patients with disease progression or improvement in health status occurring from Randomization (Day 1) to Day 28. Disease progression is defined as change in patient health status assessment from item 7 to items 1- 6 and health improvement -as change from item 7 to item 8, evaluated by the ordinal NIAID 8-Point Clinical Progression Outcomes scale collected at every visit from Day 1 through Day 45. 
The 8-category ordinal scale of patient health status ranges from:
 
1. Death;2. Hospitalized, on invasive mechanical ventilation or extracorporeal membrane oxygenation (ECMO);

		
3. Hospitalized, on non-invasive ventilation or high flow oxygen devices;4. Hospitalized, requiring supplemental oxygen;5. Hospitalized, not requiring supplemental oxygen - requiring ongoing medical care (COVID-19 related or otherwise);6. Hospitalized, not requiring supplemental oxygen - no longer requires ongoing medical care;7. Not hospitalized, limitation on activities and/or requiring home oxygen;8. Not hospitalized, no limitations on activities. 
• Changes in EQ-D5-5L (used as an indicator of symptom improvement) from randomization (Day 1) to Day 8, Day 14 and Day 28.
	To evaluate changes in inflammatory markers	
• Changes in plasma IL-6 level from randomization (Day 1) to Day 4, 8, 11, and 14.• Changes in CRP, LDH, CPK, ferritin, D-dimer from randomization (Day 1) to Day 4, 8, 11, and 14.
Study Population:	This study will enroll male and non-pregnant female patients \geq 18 years of age with moderate COVID-19. Approximately 20 outpatients will be equally randomized in two treatment arms.	
Phase:	II	
Description of Study Intervention:	CX-4945 will be administered twice a day for up to 14 days. The starting dose will be 1000 mg BID (2000 mg total daily dose).	
Study Duration:	12 months (from study initiation until completion of data analyses)	

Patient Duration:	The total duration of the treatment will be 14 days. Patients will be followed up at 28, 45 and 60 days from the start of the treatment. The total duration for each patient in the study (including screening) will be up to 67 days.
--------------------------	--

1.2. SCHEMA

1.3. SCHEDULE OF ACTIVITIES (SOA)

Table 1: Schedule of Activities

Procedure/Assessments	Screening Visit	Treatment Phase					Follow-Up ^[14]				
		Day	SV	Day 1 (Baseline)	Day 4	Day 8	Day 11	Day 14 (EOT)	Day 28	Day 45	Day 60
Window Period	D-7 to Day -1			within 7 days after SV	±1 day	±1 day	±1 day	±1 day	±3 days	±3 days	±3 days
Informed Consent [1]		X									
Eligibility Evaluation [2]		X									
Patient Demographics		X									
Medical History [3]		X									
Physical Examination		X	X[4]		X[4]		X[4]	X[4]	X[4]	X[4]	
Vital Signs [5]		X	X	X	X	X	X	X	X	X	
Assessment of COVID-19-related Symptoms [6]	X	Assessed Daily from Day 1-Day 14					X	X			
EQ-D5-5L			X		X		X	X			
Clinical Status - Ordinal 8-point Scale Assessment	X	X	X	X	X	X	X	X	X	X	
Pulse Oxygen Saturation (SpO2)	X	X	X	X	X	X	X	X	X	X	
ECG	X						X				
Laboratory Tests:											
Hematology [7]	X	X	X	X	X	X	X	X	X	X	
Blood Chemistry [8]	X	X	X	X	X	X	X	X	X	X	
Coagulation [9]	X	X	X	X	X	X	X	X	X	X	
Serum/Urine Pregnancy Test [10]	X						X				
Urinalysis [11]	X	X	X	X	X	X	X	X	X	X	
IL-6 levels			X	X	X	X	X				
Nasopharyngeal Swab Sample Collection [12]	X	X		X		X	X				
Randomization [13]		X									

IP Administration (Arm A only)		Arm A: CX-4945 1000 mg BID (Day 1-Day14)									
SOC/Supportive care (Arm A and Arm B)	X (as needed)										
Mortality Status		X	X	X	X	X	X	X	X	X	
Concomitant Medications	X	X	X	X	X	X	X	X	X		
Adverse Events		X	X	X	X	X	X	X	X	X	

- [1] Informed consent must be obtained prior to patient participation in any protocol-related activities that are not part of routine care.
- [2] Initial evaluation of patient eligibility will be performed by Investigator.
- [3] Medical history and current therapies (medications and non-medications).
- [4] Symptom-directed physical examination
- [5] Vital signs will include blood pressure, heart rate, respiration rate, and temperature.
- [6] Common COVID-19-Related Symptoms (see Appendix 3) should be assessed by patients daily from Day 1 through Day 14/EOT and at Day 28 and Day 45 Follow-up visits..
- [7] Hematology: Hemoglobin, Hematocrit (HCT), Red Blood Cells (RBC), White Blood Cells (WBC) with total and differential count, Absolute Neutrophil Count (ANC) and platelets.
- [8] Blood Chemistry:
 - Hepatic function indicators: total bilirubin, alkaline phosphatase (ALP), aspartate aminotransferase (AST), alanine aminotransferase (ALT), total protein, albumin, lactate dehydrogenase (LDH)
 - Renal function indicators: BUN, Serum creatinine, creatinine clearance, or eGFR
 - Electrolytes: sodium, potassium, chloride, total calcium and bicarbonate
 - Other: Creatine phosphokinase (CPK), C-reactive protein (CRP), serum ferritin, d-dimer
- [9] Coagulation: Prothrombin time (PT) and International Normalized Ratio (INR)
- [10] ONLY performed on women of childbearing potential.
- [11] Urine samples will be tested for color, appearance, specific gravity, pH, protein, glucose, occult blood, ketones, leukocyte esterase, nitrite, bilirubin, urobilinogen, and microscopic examination of urine sediment.
- [12] Swabs will be used for RT-PCR and quantitative virologic testing:
 - Positive RT-PCR collected within 7 days before Day 1 is required at screening for patient eligibility evaluation.
 - Nasopharyngeal swab for RT-PCR and viral load assessment should be collected at Day 1, 8, 14 and 28 visits. Samples are to be stored at -70°C and shipped to the Fulgent lab twice a month.
- [13] **Randomization:** Patient number and treatment arm allocation can be performed on Day 1
- [14] For recovered patients Follow-up visits may be performed via phone or telehealth, as appropriate

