	
evaluated daily from randomization (Day 1) through Day 14 and at Day 28 and Day 45.
 
Note: Each symptom is scored individually using the following response options and scoring values:
 
○ Items 1–18: None = 0; Mild = 1; Moderate = 2; and Severe = 3○ Items 19 and 20: Not at all = 0; 1–2 times = 1; 3–4 times = 2; 5 or more times = 3○ Items 21–22: The same as usual = 0, Less than usual = 1, NO sense of smell/taste = 2. 
Note: If some symptoms were caused by other conditions documented in the medical history and started before COVID-19 (e.g., insomnia), the patient can be considered as recovered, when these symptoms return to the previous (pre-COVID-19) value.

To evaluate preliminary evidence of anti-viral activity of CX-4945 as compared to the control arm.	
Change in virologic measure:
 
● Proportion of patients with conversion of positive RT-PCR to negative RT-PCR from Randomization (Day 1) through Day 28.● Time to SARS-CoV-2 viral clearance measured as number of days from positive RT-PCR collected at randomization (Day 1) to negative RT-PCR.● Quantitative changes in viral load from Randomization (Day 1) to Day 28. 
Note: RT-PCR/viral load tests will be performed at Randomization (Day 1) and then on Day 8, Day 14 and Day 28.

To evaluate the PK of CX-4945 when given at 1000 mg BID PO (Treatment Arm A only)	
● Plasma sample of CX-4945 are collected at the following timepoints from the first four patients randomized to treatment arm A:
○ Day 1: pre-dose, 1, 2, 3, 6 and 24 hours post Day 1 morning dose.

	
○ Day 14: pre-dose, 1, 2, 3, 6, 24, 48 and 72 hours post Day 14 morning dose. 
Note: The following PK parameters will be calculated: Cmax, Tmax, AUC_{0-t}, AUC₀₋₆, and T_{1/2}.

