### 1.4.2 Method for Time to Event Data

The endpoints about time to event data as below table will be compared between treatment groups by using log-rank test, and corresponding response proportion will be presented by using Kaplan-Meier methods.

- Time to COVID-19-Related Clinical Signs Normalization
- Time to Oxygen Saturation Level Normalization
- Time to moderate COVID-19-Related Symptoms Resolution
- Time to SARS-COV-2 Viral Clearance
- Time to Improvement on NIAID 8-Point Clinical Progression Outcomes Scale (additional analysis, not mentioned in the protocol)
- Time to Improvement on EQ-5D-5L Imaginable Health Status (additional analysis, not mentioned in the protocol)

Considering the early censor on time to response (Normalization / Recovery / Viral Clearance / Improvement) data will result in over optimistic in statistical results, two data estimation methods below will be used for the sensitive analyses. Results will be claimed as robust if the results of both methods are consistent.

Time to Response (days), Best Case Scenario  
= Days to first response for responder,  
= Days to last observation for non-responder (censored)

Time to Response (days), Worst Case Scenario  
= Days to first response for responder,  
= Days to planned last observation date (31 for EQ-5D-5L and SARS-COV-2 Viral Clearance at visit 7, 45 for others at visit 8) for non-responder (censored)

Days to first response = date of first response – the first treatment date/time + 1  
Days to last observation = date of last evaluation – the first treatment date/time + 1  
For Arm SOC, the first treatment date is the date of visit 2

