## 1.5 Method for Handling Missing Value

According to protocol, multiple imputation methods were planned to be done for efficacy evaluations using PROC MI of SAS. Since the sample size is relative small for both treatments, predictive model for multiple imputation is not realistic. Additional statistics on LOCF (Last Observation Carry Forward) data will be presented for by-visit efficacy analysis.

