## 14.2.3 Nasopharyngeal Swab RT-PCR Result and SARS-CoV-2 Viral Load

### 14.2.3.1 SARS-CoV-2 Viral Clearance and Viral Load [copies/µL]

Population: Intent-to-Treat Population / Per-Protocol Population

Characteristics	Treatment Group	Difference	P-value
--Repeat Population: <See populations above>			
. Repeat Visit:			
Visit 1 (Screening), Baseline, Visit 4 (Day 8), Visit 6 (Day 14, EOT), Visit 7 (Day 28, F1), LOCF			
N (Missing)	XXX (XXX)		
Negative	XXX (XXX.X%)		
Positive	XXX (XXX.X%)		
N (Missing)	XXX (XXX)		0.XXXX
Mean (SD)	XXX (XXX)		
Median (IQR)	XXX (XXX)		
Q1~Q3	XXX~XXX		
Min~Max	XXX~XXX		
Repeat [Baseline to Visit] except Visit 1 (Screening) and Baseline			C/F
N (Missing)	XXX (XXX)	0.XXXX	
Positive to Negative#	XXX (XX.X%)		
Positive to Positive	XXX (XX.X%)		
Diff. between groups	§C - §S		
Difference (#)	XXX%		
95% CI (#)	XXX% ~XXX%a		
Repeat [Visit - Baseline] except Visit 1 (Screening) and Baseline			TW
N (Missing)	XXX (XXX)	0.XXXX	
Mean (SD)	XXX (XXX)		
Median (IQR)	XXX (XXX)		
Q1~Q3	XXX~XXX		
Min~Max	XXX~XXX		
For W, normality is not applied			
Groups Diff	§C - §S		
Median (Asymptotic SE)	XXX		
95% CI (HL)	XXX~XXX		
For T, normality is applied			
Groups Diff	§C - §S		
Mean (SD)	XXX (XXX)		
95% CI	XXX~XXX		

a denotes CI using normal approximation for binomial proportion of #  
 Viral Load > 25,000.00 copies/µL is estimated as 25,000.00 copies/µL.  
 Baseline is Visit 2 (Day 1) data, or is Visit 1 if Visit 2 (Day 1) is null

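### A remote Day 28 visit is offered to recovered patients although that visit holds the only swab after Day 14, and the SAP's LOCF and worst-case rules count a missing swab in a Day 14-positive patient as not cleared

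*Protocol*

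**What the plan says.** **Visit mode.** In the Schedule of Activities (Protocol 1.3), the Follow-Up header over Days 28, 45 and 60 carries footnote [14]: "For recovered patients Follow-up visits may be performed via phone or telehealth, as appropriate". The summary of changes for Amendment 1 also names Day 28 among these visits. The footnote does not define recovery. Protocol 8.2.2.1 and 8.2.2.2 describe it by symptoms and by clinical signs, not by RT-PCR.

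**Swabs.** Footnote [12] of the same table says: "Nasopharyngeal swab for RT-PCR and viral load assessment should be collected at Day 1, 8, 14 and 28 visits". There is no home-swab provision and no stated exemption for remote visits.

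**Endpoints.** Two virology endpoints in Protocol 3 close at Day 28: "Proportion of patients with conversion of positive RT-PCR to negative RT-PCR from Randomization (Day 1) through Day 28" and "Quantitative changes in viral load from Randomization (Day 1) to Day 28". Time to viral clearance uses the same swabs.

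**Missing data.** SAP 1.5 sets aside the protocol's multiple imputation and states: "Additional statistics on LOCF (Last Observation Carry Forward) data will be presented for by-visit efficacy analysis". SAP table 14.2.3.1 (RT-PCR and viral load) lists its rows as "Visit 1 (Screening), Baseline, Visit 4 (Day 8), Visit 6 (Day 14, EOT), Visit 7 (Day 28, F1), LOCF", so the tests of conversion and of viral-load change are run on the LOCF row as well as on the observed Day 28 row.

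**Time to clearance.** SAP 1.4.2 gives two scenarios. A responder is counted at the first negative swab in both. A non-responder is censored at the last observation in the best case. In the worst case the time is "Days to planned last observation date (31 for EQ-5D-5L and SARS-COV-2 Viral Clearance at visit 7". Agreement between the two is to be read as robustness.

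**The concern.** Whether a Day 28 swab exists can depend on whether the patient has recovered, which happens after randomization and is something the drug is meant to influence. Clinical recovery and viral clearance are different but related, so the missing swabs are unlikely to be a random subset.

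No later swab can make up for the loss. For a recovered patient still positive at Day 14, LOCF and the worst-case rule both turn an unknown Day 28 result into a failure to clear. If one arm has more remote visits, it collects more of these assigned failures. With about 10 patients per arm, one such patient moves the arm's clearance by 10 percentage points. At stake is the reading of the antiviral endpoints, which are secondary; the primary endpoint is safety.

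**Working it through.** The plan has no figure to reproduce: Protocol 9.3 rests the sample size on clinical judgment. The check traces the rules for one patient and then sizes the effect under labelled assumptions.

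**Step 1. One patient with no Day 28 swab**

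| Last swabs | LOCF row | Time to clearance, best case | Time to clearance, worst case |
|---|---|---|---|
| Negative at Day 14 | negative | event at first negative swab | same event |
| Positive at Days 8 and 14 | positive, with Day 14 viral load | censored at about Day 14 | uncleared to Day 31 |

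Only the second row is misclassified. The observed Day 28 row omits both patients.

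**Step 2. Size within one arm**

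Assumptions, none from the documents: q = share not cleared by Day 14; r = share of those with no Day 28 swab because the visit was remote; c = share of those truly negative at Day 28. A patient once negative stays negative, and n = 10 per arm (about 20 randomized 1:1).

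- Patients wrongly carried as not cleared = 10 × q × r × c
- True clearance = 1 − q + qc
- LOCF clearance = 1 − q + qc(1 − r)

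Results:

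- Low end (0.2, 0.3, 0.5): 10 × 0.03 = 0.3 patients.
- Middle (0.4, 0.6, 0.7): 10 × 0.168 = 1.7 patients; true clearance 0.88, LOCF 0.712.
- High end (0.6, 0.9, 0.9): 10 × 0.486 = 4.9 patients.

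**Step 3. Equal true clearance, unequal remote visits**

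Take q = 0.4 and c = 0.8 in both arms, so true clearance is 0.92. Let r = 0.9 in the CX-4945 arm and 0.5 in the control arm.

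- LOCF, CX-4945: 0.6 + 0.32 × 0.1 = 0.632
- LOCF, control: 0.6 + 0.32 × 0.5 = 0.760
- False difference: −12.8 points (−6.4 at q = 0.2, −19.2 at q = 0.6)

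A simulation of 4,000 trials with 10 per arm gave worst-case Kaplan-Meier clearance of 0.636 vs 0.763 and a log-rank rejection rate of 7.4%. In the best case the rejection rate was 5.2%. The best-case Kaplan-Meier estimates were nevertheless 0.722 vs 0.903, because only 10 × 0.4 × 0.1 = 0.4 patients are expected at risk at Day 28 in the CX-4945 arm.

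With r = 0.6 in both arms, LOCF gives 0.6 + 0.32 × 0.4 = 0.728 in each. Both arms are understated and no between-arm bias arises.

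**Step 4. A real difference in recovery**

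Assume 90% (Arm A) and 60% (Arm B) are recovered at Day 28. By Day 14, 50% of recovered and 30% of unrecovered patients are negative. Of those still positive, 85% and 50% clear by Day 28. Let t be the share of recovered patients seen remotely without a swab.

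- Recovered patients truly clear: 0.5 + 0.5 × 0.85 = 0.925. Unrecovered: 0.3 + 0.7 × 0.5 = 0.65.
- True clearance: A = 0.9 × 0.925 + 0.1 × 0.65 = 0.8975; B = 0.6 × 0.925 + 0.4 × 0.65 = 0.815. Gap 8.25 points.
- LOCF: A = 0.8975 − 0.3825t; B = 0.815 − 0.255t. Gap = 0.0825 − 0.1275t, zero at t = 0.647.
- Worst-case Kaplan-Meier at Day 31 equals the LOCF figure, since nobody is censored earlier.
- Observed-case A = [0.9(1 − t) × 0.925 + 0.065] / [0.9(1 − t) + 0.1]; B is [0.6(1 − t) × 0.925 + 0.26] / [0.6(1 − t) + 0.4].
- Best-case Kaplan-Meier = 1 − (share positive at Day 14) × (1 − Day 28 clearance among those swabbed). The share positive at Day 14 is 0.52 in A and 0.58 in B.

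| Analysis | t = 0.5 (A vs B) | Gap | t = 1 (A vs B) | Gap |
|---|---|---|---|---|
| Truth | 89.8% vs 81.5% | 8.3 | 89.8% vs 81.5% | 8.3 |
| LOCF and worst case | 70.6% vs 68.8% | 1.9 | 51.5% vs 56.0% | −4.5 |
| Observed Day 28 | 87.5% vs 76.8% | 10.7 | 65.0% vs 65.0% | 0.0 |
| Best-case Kaplan-Meier | 87.9% vs 78.1% | 9.8 | 74.0% vs 71.0% | 3.0 |

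LOCF and the worst case shrink the gap. Observed-case and best-case exaggerate it at t = 0.5 and shrink it at t = 1. The observed-case gap returns to its true value where 27s² − 29s + 2 = 0 with s = 1 − t. That gives s = 2/27, or t of about 0.93.

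**The case against.** **The footnote is permissive.** It allows a remote visit where appropriate and waives no procedure; footnote [12] still stands. This is right: a reader might infer that Day 28 swabs will be missing, or missing for many patients, but the documents show only that they can be. Protocol 7.3 and the opening of section 8 also allow remote contact for other reasons, so missing swabs need not be confined to recovered patients.

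**LOCF is additional and the worst case is paired.** The SAP calls LOCF an additional statistic and shows the observed Day 28 row beside it. The best-case rule already censors these patients at their last swab, so there is no need to alter the worst case, which is meant to be extreme. That stands. The pairing is still not a full safeguard: at t = 0.5 in Step 4 both scenarios favor Arm A, yet one overstates the gap and the other understates it.

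**Direction.** A reader might infer a general bias toward no effect, or a reversal of sign. Neither follows. Observed-case and best-case results can exaggerate the effect. Reversal under LOCF needs more than about 65% of recovered patients to go without the swab, on top of an assumed 90% vs 60% recovery gap. If 60% rather than 50% of Arm A's recovered patients were negative by Day 14, LOCF at t = 1 would give 0.9 × 0.6 + 0.065 = 60.5% vs 56.0%, with no reversal.

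**SpO2 and laboratory data.** A reader might extend the point to these. The laboratory and SpO2 tables (SAP 14.3.2 to 14.3.6 and 14.3.8) have no LOCF row, the inflammatory-marker endpoints stop at Day 14, and a patient recovered by signs has already met the SpO2 threshold. Missing Day 28 laboratory results are a gap in safety data. A patient judged recovered on symptoms alone could lack a SpO2 reading, which is one more reason to define the term.

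**Existing tables.** SAP 14.1.3 counts remote visits by arm and 14.2.3.1 shows missing counts by arm. Neither links visit mode to missing swabs or to the last PCR result.

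**Conclusion.** The concern holds in a limited form. Footnotes [12] and [14] are unreconciled, so the swab that closes two virology endpoints can be missing for a reason tied to a post-randomization outcome. For a patient still positive at Day 14, LOCF and the worst-case rule then record failure to clear. These two analyses understate clearance, and other things equal they do so more in the arm with more remote visits. The direction of bias in the observed-case and best-case results is not fixed.

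The size cannot be established. The 0.3 to 4.9 patients per arm rests on assumed ranges for q, r and c, and the Step 4 table on a single assumed scenario. Patients negative by Day 8 or Day 14 are unaffected in the time-to-clearance analysis. This is a worthwhile, inexpensive correction to secondary endpoints in a proof-of-concept trial of about 20 patients; it does not touch the primary safety objective.

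**What to change.** **Protocol 1.3.** Reconcile footnotes [12] and [14] so that a remote Day 28 visit does not waive the scheduled swab for a patient whose last swab was positive, and define recovery for this purpose. Days 45 and 60 may stay remote, since no swab is due then.

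**SAP 1.5 and 14.2.3.1.** Remove RT-PCR and viral load from the LOCF row. Report missing Day 28 swabs by arm, visit mode and last PCR status, so that readers of the observed-case row can judge it.

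**SAP 1.4.2.** Keep the best-case and worst-case pair as defined. Add that agreement between them is not proof of robustness when Day 28 swabs are missing among recovered patients.

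**Cost.** A few recovered but still-positive patients attend a visit already in the schedule, to be weighed against the protocol's wish to limit face-to-face contact because of infection risk. The footnote change needs IRB approval (Protocol 11.2). SAP section 2 expects the last patient to leave on 7 October 2021, so the footnote change may come too late for this trial. The SAP changes do not depend on that; they need some rewording and one extra table. With no Day 28 swab missing (r = 0), the misclassification in Step 2 is zero.
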